## **10.2 Interim Analyses**

No interim analyses are planned for this study.

## **10.3 Determination of Sample Size**

We estimate that more than 10 patients per day attend consultations for cancer in Medical Oncology, Radiotherapeutic Oncology, Hematology and Palliative Care Departments and around 5 patients in Pain Units, and each site shall have a recruitment period of 1 month. Cancer breakthrough pain is a common and incapacitating subtype of pain that affects a percentage of patients with cancer that varies between 40% and 90% according to different publications [1, 2]. Conservatively, we hope to detect the prevalence in 50% of patients, and we estimate that at each site a total of approximately 200 patients, or around 13,200 across the 66 planned sites, will be interviewed on the prevalence of breakthrough pain. This sample will enable us to detect the prevalence of breakthrough pain with a 95% confidence interval and precision of  $\pm 1\%$ .

For the assessment of the secondary objective, i.e., characterising the breakthrough pain based on aetiology, underlying pathology and other clinical characteristics (type of breakthrough pain, number of episodes per day, duration and intensity, comorbidities and baseline pain management), if we consider the detection of common characteristics in at

least 10% of patients in our population to be representative, it will be necessary to recruit 529 patients in order to detect said characteristics with a 95% confidence interval and precision of  $\pm 2.5\%$ .

All patients recruited for characterisation of breakthrough cancer pain will be newly diagnosed and previously untreated for breakthrough cancer pain, although patients may be recruited who have been treated for breakthrough cancer pain in the past but are not currently being treated (at least 1 month wash-out) to avoid possible distortions in the classification of pain that may result from treatment.

Patients eligible to participate in the study must meet all the selection criteria, have a confirmed diagnosis of breakthrough cancer pain based on the Davies algorithm and must have given their informed consent in writing.

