## 2 Introduction

Oncology consultations are generally short in duration (20-30 minutes). The primary consideration for most oncologists during this time is treatment of the tumour: the choice of treatment to be administered to the patient (chemotherapy, radiotherapy, etc.), the administration of recommended treatment, and the monitoring and control of the efficacy and safety of these treatments, principally in relation to tumour response and survival [4].

Symptoms, such as pain, are often given less attention during diagnosis and treatment. Pain is one of the most common symptoms of cancer [5-7]. However, published estimates of the prevalence of pain in outpatients are inconsistent and vary between 18% and 62%, probably due to differences between the various selection criteria, the use of dissimilar assessment tools and/or different tumour stages [5-7].

Breakthrough pain is understood as the temporary exacerbation of pain occurring either spontaneously or in relation to a specific, predictable or unpredictable trigger in spite of relatively stable and adequately controlled baseline pain.

Breakthrough cancer pain is a common and distressing subtype of pain that affects a percentage of patients with cancer that varies between 40% and 90% according to different publications [1, 2]. The type of breakthrough pain seen in cancer is described as “a temporary increase in pain with an intensity above that considered moderate, overlying baseline pain of moderate or low intensity” in cancer patients treated with opioids [8].

Breakthrough cancer pain is a high intensity, short duration pain that manifests in several daily episodes and does not respond to normal treatment. The clinical approach to breakthrough cancer pain is changeable. The data show that daily exacerbations of pain need to be monitored closely, differentiating where possible between fluctuations in baseline pain and the end-of-dose effect [9].

The causes of cancer breakthrough pain are the same as those of cancer pain, and they can be related to the neoplasm, with diagnostic tests, treatment or other concomitant problems concurrent with cancer [10]. In terms of physiology, breakthrough pain may be nociceptive, neuropathic or mixed [10].

Even today, clinical focus in breakthrough pain varies considerably between clinics, from complete denial of its existence to overestimation [9].

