### **3 Study Objective(s)**

#### **Primary objective**

- To estimate the prevalence of breakthrough cancer pain in an unselected representative cohort of cancer outpatients with or without pain who attend consultations at Medical Oncology, Hematology, Radiotherapeutic Oncology Departments, Pain Units and Palliative Care Units at participating sites. The estimated annual prevalence will be calculated relative to the population of cancer patients with or without pain seen in participating practices over one month.

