## 6.2 Discussion of Study Design

The study’s limitations derive from its design as a cross-sectional, non-PAS, non-interventional study in which the proportion of patients with breakthrough cancer pain attending consultations in Medical Oncology, Hematology, Radiotherapeutic Oncology Departments, Pain Units and Palliative Care Units may not be representative of the general population of cancer sufferers. However, it will allow us to obtain a valid estimate in the population attending said consultations.

A further limitation relates to the extrapolation of the results to the national population, as although 66 sites distributed throughout the country will participate in the study, it is possible that these may not be representative of Spain as a whole, due to the characteristics of the sites selected.

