As this is an observational, cross-sectional, non-PAS and non-interventional study, it will not under any circumstances involve changes to normal clinical practice or the performance of tests not considered normal clinical practice. Throughout the study, each investigator must treat the patients diagnosed with breakthrough cancer pain and recruited to the study, whether treatment-naïve or currently untreated, after characterising their pain, in accordance with the criteria habitually used in clinical practice for patients of this type.

The study period is initially estimated at 12 months for data collection. This corresponds to the recruitment and data entry periods, as due to the study's characteristics no follow-up period is planned. Data entry in the database, analysis and the drafting of the final report will be carried out once the recruitment period is concluded. If, following the recruitment period planned in the protocol (maximum 3 months), the expected number of patients for the characterisation of breakthrough pain has not been reached, recruitment will be continued competitively within each specialty (120 patients included in each specialty except 60 patients in hematology), until 529 patients have been recruited.

The investigator will be responsible for ensuring the correct completion of all sections of the Case Report Form.

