### 5.1. Primary objective analysis

In the prevalence study the following variables will be collected:

- Patient with cancer pain: yes/no
- Breakthrough cancer pain: yes/no
- Diagnostic of BCP: Previously diagnosed; Diagnosed during the visit (according Davies algorithm)
- Date of visit.
- Age.
- Gender.
- Karnofsky PS (0 to 100).
- Type of tumour: head and neck, colorectal, esophagus, stomach, liver, leukemia, lymphoma, breast, multiple myeloma, bone and muscular, ovarian, pancreas, prostate, lung, kidney, central nervous system, testicle, uterus, bladder and other).
- Stage (I-IV).

The prevalence of breakthrough cancer pain and corresponding 95% confidence interval (95%CI) will be calculated as the percentage of subjects presenting breakthrough pain among patients with cancer pain controlled with opioids, collected by all investigators over one month.

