#### Formula:

Prevalence of breakthrough cancer pain (%) = [Number of patients with breakthrough cancer pain / total number of patients registered with cancer pain] x 100.

The estimated annual prevalence will be calculated relative to the population of cancer patients with or without pain seen over one month.

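### The stated ±1% precision holds for all cancer attenders, but the primary analysis divides by a smaller group for which no precision is given

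*Protocol*

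**What the plan says.** **Precision.** Protocol 10.3, the protocol summary and SAP 3.6 assume about 200 people per site attending for cancer over one month, hence about 13,200 at 66 sites, with prevalence set at 50%. They conclude: "This sample will enable us to detect the prevalence of breakthrough pain with a 95% confidence interval and precision of" ±1%.

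**Denominator.** Three appear in the documents.

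- All cancer outpatients, in pain or not. The primary objective in Protocol 3, repeated in SAP 3.5, concerns an "unselected representative cohort of cancer outpatients with or without pain who attend consultations".
- Opioid-controlled cancer pain. This is the primary variable in the protocol summary (criteria for evaluation, statistical methods), Protocol 7 and Protocol 10.1. SAP 5.1 (primary objective analysis) says the same: "The prevalence of breakthrough cancer pain and corresponding 95% confidence interval (95%CI) will be calculated as the percentage of subjects presenting breakthrough pain" in that group.
- Registered cancer pain, with no opioid condition. The formula that follows in SAP 5.1 is "Number of patients with breakthrough cancer pain / total number of patients registered with cancer pain".

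Prevalence over all cancer patients, which is what the ±1% describes, appears in SAP 5.2 as a secondary result.

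**Share in pain.** The sample size sections give no planning value. Protocol 2 says that "published estimates of the prevalence of pain in outpatients are inconsistent and vary between 18% and 62" per cent.

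**Target.** Protocol 6.2 claims a valid estimate for people attending these consultations and says of the sites that "it is possible that these may not be representative of Spain as a whole".

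**The concern.** The 13,200 are people attending for cancer, and the prevalence form records cancer pain as yes or no, so the count includes people without pain. Both denominators used for the primary analysis are therefore subsets of it. A precision worked out for the whole group does not describe an interval computed in a subset, and no passage gives the expected size of either subset.

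At stake is how the primary result will be read. The sample size text promises ±1 point, and the interval that the SAP formula produces may be up to about twice as wide. The percentage itself is not affected.

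**Working it through.** **Formula.** Half-width in points = 196 × √(p(1−p)/n); at p = 0.5 this is 98/√n. Patients are treated as independent.

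**1. The plan's own figure.**
- Needed for ±1 at p = 0.5: 1.96² × 0.25 / 0.01² = 9,604.
- 66 × 200 = 13,200 gives 98/√13,200 = ±0.85.
- Protocol 10.3 expects more than 10 a day elsewhere "and around 5 patients in Pain Units, and each site shall have a recruitment period of 1 month". With 20 working days (assumed), a Pain Unit sees about 100. With 24 Pain Units (step 3), the total is 42 × 200 + 24 × 100 = 10,800, giving ±0.94.

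The ±1% is met for all cancer attenders either way.

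**2. Cancer-pain denominator, cited range at every site.** ±1 needs 9,604 / 13,200 = 73% of attenders in pain.
- 18% in pain: n = 2,376, ±2.01.
- 62% in pain: n = 8,184, ±1.08.

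**3. The same, with everyone in Pain Units in pain.** The number of Pain Units is inferred from Protocol 7, where "recruitment will be continued competitively within each specialty (120 patients included in each specialty except 60 patients in hematology". At 10 patients per investigator (5 in Pain Units) and one investigator per site, this is 3 × 120/10 = 36 sites in Medical Oncology, Radiotherapeutic Oncology and Palliative Care, 60/10 = 6 in Hematology and 120/5 = 24 Pain Units. The total of 66 agrees with the plan. The other 42 sites see 42 × 200 = 8,400.

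| Patients per Pain Unit (assumed) | In pain elsewhere | n in pain | Half-width at 50% |
|---|---|---|---|
| 100 | 18% | 2,400 + 1,512 = 3,912 | ±1.57 |
| 100 | 62% | 2,400 + 5,208 = 7,608 | ±1.12 |
| 200 | 18% | 4,800 + 1,512 = 6,312 | ±1.23 |
| 200 | 62% | 4,800 + 5,208 = 10,008 | ±0.98 |

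To reach 9,604, the share in pain elsewhere must be (9,604 − 4,800)/8,400 = 57% with 200 per Pain Unit, or (9,604 − 2,400)/8,400 = 86% with 100.

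**4. Prevalence other than 50%.** At p = 0.9, n = 3,912 gives 196 × √(0.09/3,912) = ±0.94, and n = 2,376 gives ±1.21. Moreover, 50% cannot serve every denominator: half of 13,200 attenders is 6,600 with breakthrough pain, yet at 18% only 2,376 would be in pain at all.

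**5. Opioid-controlled pain.** This is a further subset, so n falls and the half-width at a given p grows. The documents do not give its share, so no figure is offered.

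**The case against.** The strongest reply is that the ±1% is correct for what it describes. It matches the primary objective, and the result over all cancer patients will be reported with its own interval. That stands, and it shows that the root problem is three competing primary denominators rather than an arithmetic error. It also means that one cannot infer that the sample is too small: 13,200 comes from expected attendance over a month, and the ±1% is presented as a consequence.

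The size of the shortfall is also open to argument. More than 10 a day makes 200 per site nearer a floor outside Pain Units, Palliative Care may have more patients in pain than the cited outpatient range, and prevalence well away from 50% narrows the interval. At 62% in pain the results are ±1.12 to ±0.98, close to the stated figure. These points stand as reasons to report a range. They do not supply the missing precision.

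A reader might also infer that the intervals are invalid because patients are grouped in 66 sites. The documents do not support that as it stands. SAP 3.5 refers to participating sites and practices, and Protocol 6.2 names extrapolation to Spain as a limitation. For a description of those sites, no between-site allowance is needed. The visible text names no interval method (the SAP table index is redacted) and gives no intra-site correlation (ICC). The study title and the word representative in the objective invite a wider reading, so the target should be stated, but undercoverage is not shown.

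**Conclusion.** The point holds as a mismatch between the stated precision and the primary analysis. For all cancer attenders the plan delivers ±0.85 to ±0.94, better than promised. For patients with cancer pain, at 50% prevalence and with independent patients, it delivers ±2.01 to ±1.08 if the cited pain range applies everywhere, and ±1.57 to ±0.98 if everyone in Pain Units has pain.

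These figures rest on the outpatient range in Protocol 2, the inferred 24 Pain Units and the assumed 100 to 200 patients in each. The shortfall is material at low shares in pain and negligible near the top of the range. The study is descriptive with no decision threshold, so the consequence is a misstated precision for the primary result, not a wrong decision.

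**What to change.** 1. Reconcile the objective (Protocol 3, SAP 3.5), the primary variable (protocol summary, Protocol 7 and 10.1, SAP 5.1 text) and the SAP 5.1 formula, and name one primary denominator. If it is opioid-controlled pain, confirm that the prevalence form identifies those patients, because the variables listed in SAP 5.1 and 5.2 include no opioid item.
2. In Protocol 10.3, the protocol summary and SAP 3.6, replace the single ±1% with the expected number of patients and half-width for the primary denominator and for each other denominator reported. Use a stated range for the share in pain (and on opioids) and a prevalence that fits each denominator.
3. State in SAP 5.1 that the intervals refer to patients seen at the participating sites. Only if wider inference is intended, use a site-clustered variance stratified by specialty and give precision over a stated ICC range. For illustration, with 13,200 patients, 200 per site and p = 0.5, the design effect is 1 + 199 × ICC: an assumed ICC of 0.001 gives 1.199 and ±0.93, and 0.01 gives 2.99 and ±1.47. This would not cure unrepresentative site selection.

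The cost is a few changes of wording and a less favourable stated precision. Restating the precision needs no change to the sample size or to the data collected.

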**Number of subjects**

We estimate that more than 10 patients per day attend consultations for cancer in Medical Oncology, Radiotherapeutic Oncology, Hematology and Palliative Care Departments and around 5 patients in Pain Units. Breakthrough cancer Pain (BCP) is a common and incapacitating subtype of pain that affects a percentage of patients with cancer that varies between 40% and 90% according to different publications. Conservatively, we hope to detect the prevalence in 50% of patients, and we estimate that at each site a total of approximately 200 patients, or around 13,200 across the 66 planned sites, will be interviewed on the prevalence of breakthrough cancer pain. This sample will enable us to detect the prevalence of breakthrough pain with a 95% confidence interval and precision of  $\pm 1\%$ .

For the assessment of the secondary objective, i.e., characterising the breakthrough pain based on aetiology, underlying pathology and other clinical characteristics, if we consider the detection of common characteristics in at least 10% of patients in our population to be representative, it will be necessary to recruit 529 patients in order to detect said characteristics with a 95% confidence interval and precision of  $\pm 2.5\%$ .

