  - Alberta Breakthrough Pain Assessment Tool for the assessment of breakthrough pain in cancer patients
  - Brief Pain Inventory (BPI)

- Numerical Rating Scale (NRS) for the assessment of pain intensity
- Quality of life assessment:
  - SF-12 Questionnaire
  - Karnofsky performance status

Using an anatomical drawing or doll, the exact location in which the patient presents the breakthrough cancer pain crisis will be identified, determining whether one or several breakthrough pains are involved.

A series of graphs illustrating various profiles for the behaviour of breakthrough pain will then be used, in order to determine which type(s) of breakthrough pain each patient recruited to the study presents.

[figure not shown]
The following graphs will be used:

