#### 6.4. Breakthrough cancer pain

We will characterize the breakthrough pain based on:

- Etiology (nociceptive, neuropathic or mixed)
- If nociceptive,
  - Somatic nociceptive or visceral nociceptive (question Q2 of Alberta's questionnaire to be completed by physician or nurse).
- Trigger factor of breakthrough pain (spontaneous pain or idiopathic pain / incident pain).
  - If incident pain,
    - Volitional, non-volitional and procedural.
- Location and type of breakthrough pain (BCP type I to IV).
- Pain intensity (Question 3 of BPI scale: Please rate your pain by circling the one number that best describes your pain at its least in the past 24 hours).

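### The ±2.5% precision claimed for characteristics present in at least 10% of patients holds only near 10% or above about 90%; 529 patients give about ±4.0 points at 33% and ±4.3 at 50%

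*Protocol*

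**What the plan says.** The sample size for the characterisation study is justified by one sentence, which appears in the Protocol Summary (Number of subjects), in Protocol 10.3 and, in near-identical words, in SAP 3.6. It starts from the condition "if we consider the detection of common characteristics in at least 10% of patients in our population to be representative" and concludes that "it will be necessary to recruit 529 patients in order to detect said characteristics with a 95% confidence interval and precision of" ±2.5%. The only proportion named is 10%. No precision is given for commoner characteristics, and no finite-population correction is mentioned.

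The characteristics to be described are listed in SAP 6.4. They include aetiology in three categories ("Etiology (nociceptive, neuropathic or mixed"), trigger in two ("Trigger factor of breakthrough pain (spontaneous pain or idiopathic pain / incident pain") and breakthrough pain types I to IV. For the types, Protocol 7 (Description of the visit) uses graphs "in order to determine which type(s) of breakthrough pain each patient recruited to the study presents". The percentage of patients with each type is a named secondary objective in Protocol 3 and SAP 3.5. SAP 6.1 plans frequencies and percentages for categorical variables, and the readable text of SAP 6 to 8 plans no confidence intervals for them.

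**The concern.** The phrase that sets the threshold is a lower bound, and the precision is then attached to all characteristics that meet it. For a proportion, the confidence interval is widest at 50%. A calculation at 10% therefore gives the most favourable half-width anywhere between 10% and 90%, and it cannot be carried upward from there.

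The paragraph before it in Protocol 10.3 handles this correctly. It plans the prevalence estimate at 50% and calls that conservative, so its ±1% holds at any prevalence. A reader coming from that paragraph would expect the next one to work the same way.

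This is the only precision stated for the characterisation results, and Protocol 12 says that the study is to be published. If the sentence is quoted as it stands, the main classification percentages will look more precise than they are.

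**Working it through.** **Inputs.** The 95% confidence level (z = 1.96), target half-width of 2.5 points, design proportion of 10% and n = 529 come from Protocol 10.3. The screened cohort of about 13,200 and the expected 50% prevalence come from the same section. The categories come from SAP 6.4. Simple random sampling is assumed, since no design effect is stated.

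**Reproducing 529.** The usual formula is n = z²p(1−p)/d².

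- At p = 0.10 and d = 0.025: 3.8416 × 0.09 / 0.000625 = 553.2, so 554.
- With a finite-population correction on 13,200: 553.2 / (1 + 552.2/13,200) = 531, within two patients of 529.
- With a correction on the expected 6,600 breakthrough-pain cases (50% of 13,200): 553.2 / (1 + 552.2/6,600) = 511, which does not match.

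So 529 is about right at exactly 10%, and is approached most closely with a correction that the documents do not state. The gap to 554 is small and nothing below depends on it.

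**Half-width with 529 patients.** Half-width = 1.96 × √(p(1−p)/529). The corrected column multiplies this by √((13,200−529)/13,199) = 0.980.

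| True share | Half-width (points) | With correction on 13,200 |
|---|---|---|
| 10% | 2.56 | 2.51 |
| 20% | 3.41 | 3.34 |
| 25% | 3.69 | 3.62 |
| one third | 4.02 | 3.94 |
| 50% | 4.26 | 4.17 |
| 90% | 2.56 | 2.51 |

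Other interval methods change little. Wilson half-widths are 2.56 points at 10%, 4.00 at one third and 4.25 at 50%. Clopper-Pearson gives about 2.65, 4.10 and 4.35.

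**Where ±2.5 is met.** This needs p(1−p) ≤ 0.025² × 529 / 1.96² = 0.0861, so p ≤ 9.5% or p ≥ 90.5%. With the correction on 13,200 the limits are about 10.0% and 90.0%.

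**Where the planned results must fall.** If every patient is classified, the largest of k exhaustive categories holds at least 1/k of patients:

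- aetiology (k = 3): at least 33%;
- spontaneous versus incident (k = 2): at least 50%;
- types I to IV (k = 4): at least 25%. This remains true if a patient can have more than one type, because the shares then add up to 100% or more.

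In each classification, the percentage for the largest category misses ±2.5 points unless that category exceeds about 90%. This follows from counting and needs no guess about the results.

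**Size of the understatement.** 3.69/2.5 = 1.5 at 25%, 4.02/2.5 = 1.6 at one third, and 4.26/2.5 = 1.7 at 50%.

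**What ±2.5 everywhere would need.** At p = 0.50: 3.8416 × 0.25 / 0.000625 = 1,536.6, so 1,537 patients. With the correction on 13,200 it is 1,377.

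**Comparison with the prevalence paragraph.** 1.96 × √(0.25/13,200) = 0.85 points at 50%, so under the same assumption ±1% holds at every proportion.

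**The case against.** The best defence is that the 10% threshold only defines which characteristics are common enough to matter, and that 10% is simply the design value. On that reading the claim is ±2.5% at 10%, and the true ±2.56 is essentially right. The wording is loose enough to allow this. But the sentence ties the precision to all the characteristics so defined, and nothing elsewhere limits it to 10% or gives a figure for higher shares. If only 10% was meant, saying so costs the sponsor nothing.

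It can also be said that the study is descriptive, that no interval is planned for these percentages, and that anyone with n and a percentage can compute one. This is true and limits the consequence to how the results are presented and read. It does not make the stated precision correct, and in a descriptive study precision is the whole justification for the sample size.

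A further objection does stand: the half-widths given here are themselves favourable. Patients are recruited at 66 sites, about 8 per site (529/66). With an assumed intra-site correlation of 0.01 to 0.05, the design effect 1 + 7 × ICC is 1.07 to 1.35, and ±4.26 becomes about ±4.4 to ±5.0. The documents give no such correlation, so this is only an illustration. It does mean that any replacement sentence should state its sampling assumption.

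**Conclusion.** The concern holds. As worded, the plan claims ±2.5% for characteristics present in 10% of patients or more, and 529 patients do not provide that between 9.5% and 90.5%. The half-width is ±2.56 points at 10%, about ±4.0 at one third and about ±4.3 at 50%. A finite-population correction on 13,200 lowers the last two only to 3.94 and 4.17. These figures assume simple random sampling of 529 analysed patients, and the statement about largest categories assumes that every patient is classified. The sample size is not called into question, and no test or decision uses the figure. The fault is a stated property that the design lacks, in the only precision statement for the characterisation results, and it should be corrected.

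**What to change.** Keep n = 529. In the Protocol Summary, Protocol 10.3 and SAP 3.6, replace the sentence with:

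*Assuming simple random sampling, 529 patients give a 95% CI half-width of about ±2.6% for a characteristic present in 10% of patients, rising to about ±4.3% for one present in 50%.*

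If a finite-population correction was used to reach 529, state it together with the population size. Optionally, report 95% CIs for the SAP 6.4 percentages, for which the CAT3 table shell in the SAP already has the columns.

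The cost is one sentence in three places, with no change to recruitment or data collection. The stated precision becomes less favourable, up to ±4.3 instead of ±2.5. Enlarging the study to 1,537 patients to reach ±2.5 at 50% would be out of proportion for a descriptive objective.
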